- o History of past use of other anticoagulants
- Pregnancy and lactation status at the time of prescription
- Time and type of any surgery (including orthopaedic surgery) during the treatment with edoxaban
- Presence of mechanical heart valves
- Pertinent lab tests upon availability including liver function test, CrCl test and/or Glomerular Filtration Rate (GFR) pertaining to possible hepatic or renal impairment.

• Drug utilisation:

- o Edoxaban prescription:
 - start and end date/ongoing treatment (including repeated prescriptions if any)
 - daily dose (30 mg, 60mg, other) at the beginning of the treatment and afterwards
 - reason for use
 - reason of discontinuation (if applicable)
- Concomitant medications (including if patient is using dual antiplatelet therapy).

Health Care Professional (HCP) Educational Material knowledge assessments

- Survey administration variables
- Description of survey participants
- Assessment of knowledge of the key messages of the educational program.

Data Sources

DUS

This study is a retrospective chart review. The identified local site staff will review the medical charts of all patients that have been prescribed edoxaban, over the given time period and extract the desired data elements. The data will be entered pseudonymised into electronic Case Report Forms (eCRFs) via a secure web-based EDC system. In sites that do not have the capabilities to access the internet to enter data, a provision will be made to collect pseudonymised data recorded on paper CRFs and entered into the study database by the Sponsor or designee (e.g. Contract Research Organization, (CRO)) on behalf of the site staff.

To assess the representativeness of the sampled patient population, a screening log of all patients prescribed with edoxaban will be maintained by the site staff, including patient's age and gender, and whether the patient's chart data was included in the DUS or not. For patient charts that

were not captured in the DUS, the reasons for non-inclusion will be documented on the screening log.

Educational Material Evaluation Survey

At the prescribers' primary contact (index date), the physicians will be requested to express their preferences for a means of direct-to-physician contact (email or telephone) in order to complete the survey.

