9.3. Variables

The following information will be entered in the CRF

I. Site/ Physicians' characteristics

To evaluate the diversity of sites the following information will be collected for each participating site from the site feasibility questionnaire:

- Geographic location of physician site;
- Profession or area of primary practice (e.g., GPs, cardiologists, and other specialists;
- Patient volume (i.e., number of patients and estimated number of patients using edoxaban).

II. Edoxaban treated patient data

1. Demographics and medical history:

- Birth (year/month) or age
- Race/ethnicity (where permitted)
- Height
- Body weight
- Smoking status
- Alcohol consumption
- Diagnosis
- Risk factors and treatment (pharmacological or non-pharmacological) history pertaining to edoxaban treatment
- Cardiovascular comorbidities (including valvular disease) and other relevant somatic comorbidities
- History of haemodialysis

- Relevant familial medical history
- History of past use of other anticoagulants
- Pregnancy and lactation status at the time of prescription
- Time and type of any surgery (including orthopaedic surgery) during the treatment with edoxaban
- Presence of mechanical heart valves
- Pertinent lab tests upon availability including liver function test, CrCl and/or Glomerular Filtration Rate (GFR) pertaining to possible hepatic or renal impairment.

2. Drug utilisation:

- Edoxaban prescription
 - start and end date/ongoing treatment (including repeated prescriptions if any)
 - o daily dose (30 mg, 60mg, other) at the beginning of the treatment and afterwards
 - o reason for use
 - o reason of discontinuation (if applicable)
- Concomitant medications (including if patient is using dual antiplatelet therapy)

III. HCP Educational Material knowledge assessments

1. Survey administration variables:

- o Number of physicians in sample, in total and by key characteristic;
- o Number of physicians attempted to contact
- o Number of physicians effectively contacted
- Number of contacted physicians who agreed to participate
- o Of those agreed to participate, number who completed survey.

2. Description of survey participants

- Medical specialty
- Country
- Setting (type, geography)
- o Experience with edoxaban (yes/no and if yes number of months)
- o Receipt of educational material (yes/no) and time elapsed since its return.

3. Assessment of knowledge of the key messages of the educational program:

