The survey will be administered either by phone or on line through a secure unique web link concomitantly at the time of the site initiation visit, thus minimizing the impact of any previous reading of the Educational Material by the physician. Six months later, the same Survey will be administered de novo.

The afore-described strategy, together with a comparative analysis of respondents and non-respondents' characteristics, is expected to minimize and detect any response bias or trend among the survey population.

The Educational Material will be distributed to all physicians prior to edoxaban availability and irrespectively from the participation in the DUS. However, investigators participating in the DUS may take part in the survey to assess the physicians' level of awareness and understanding of the content of the educational material/SmPC, including:

- Indications
- o Dosing recommendations and dose reduction
- Populations at higher risk of bleeding
- o Information on switching patients to or from edoxaban
- o Perioperative management
- Temporary discontinuation
- Overdose
- Bleeding complications
- Coagulation testing

Physicians will not be individually assessed. Results will be reported in aggregate form only and not linked to any personal identifier. All information collected during the course of the survey will be kept strictly confidential.

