APPENDIX 2. LIXIANA® - SURVEY QUESTIONNAIRE

Thank you for participating in this voluntary survey to monitor the use of edoxaban in Europe. Please answer each question/statement as honestly as possible. You will not be individually assessed as results will be reported in aggregate form only and not linked to any personal identifier. All information collected during the course of the survey will be kept strictly confidential.

Part I – Edoxaban utilisation

rt I	- Euoxana	in utilisation
1.		g the indications for which Lixiana is approved in the European Union icate if the following sentences are true (T) or false (F):
		Lixiana is indicated in the prevention of stroke in adult patients with nonvavular atrial fibrillation with or without risks factors Lixiana is indicated in the prevention of systemic embolism in adult
	0.	patients with nonvalvular atrial fibrillation with one or more risk factors
	c.	Lixiana is indicated in the treatment of deep vein thrombosis (DVT) and pulmonary embolism (PE) in adults
	d.	Lixiana is not indicated in the prevention of recurrent DVT and PE in adults
	e.	Lixiana is indicated in the prevention of VTE in subjects undergoing orthopaedic surgery
	f.	Lixiana is indicated in the prevention of atherothrombotic events after acute coronary syndrome
2.		g the recommended dosing of Lixiana, please indicate if the following are True (T) or false (F):
	a.	In patients with mild to moderate hepatic impairment, the recommended daily dose is of 30mg
	b.	In patients with normal renal and hepatic function, the recommended daily dose is of 60mg
	c.	In patients with moderate to severe renal impairment as defined by a creatinine clearance between 15 and 50 mL/min, the recommended daily dose is of 30mg
	d.	Lixiana has to be taken outside of meals
	e.	The duration of treatment with Lixiana is well defined and independent of transient or permanent risk factors
	f.	Co-administration with cyclosporine does not require any adjustment in the dose of Lixiana

- 3. Lixiana is contraindicated or not recommended in the following special patient populations (please select all that apply):
 - a. Severe hepatic impairment
 - b. Elevated liver enzymes ALT/AST 2x ULN
 - c. Hepatic disease associated with coagulopathy and clinically relevant bleeding
 - d. In co-administration with low dose ASA ($\leq 100 \text{mg/day}$)
 - e. Uncontrolled severe hypertension
 - f. Patients with a body weight $\leq 60 \text{ Kg}$

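### The knowledge survey is taken by telephone or web link as the physician prefers, with no request to answer unaided and no listed mode variable, so scores may be overstated and the stated bias controls would not show it

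*Protocol*

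**What the plan says.** All references are to the protocol.

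- **Mode.** Section 9.4, Educational Material Evaluation Survey: "The survey will be administered either by phone or on line through a secure unique web link". In the Summary (Data Sources), "the physicians will be requested to express their preferences for a means of direct-to-physician contact (email or telephone) in order to complete the survey". The physician's preference therefore guides the mode.
- **Timing.** The first round takes place "concomitantly at the time of the site initiation visit, thus minimizing the impact of any previous reading of the Educational Material by the physician". For the second round: "Six months later, the same Survey will be administered de novo". No visit is mentioned for that round.
- **Instruction.** The Appendix 2 introduction says: "Please answer each question/statement as honestly as possible". It does not ask the physician to put the Prescriber's Guide or the SmPC aside.
- **Variables.** Section 9.3, III.1 counts physicians in the sample, those approached, those reached and those agreeing, and ends with "Of those agreed to participate, number who completed survey". III.2 describes specialty, country, setting, experience and receipt of the material. Mode is in neither list.
- **Analysis.** Section 9.7 presents survey results overall, by country and by an open list of key characteristics. Mode is not named.
- **Bias claim.** Section 9.4 expects its strategy, together with a comparison of respondents and non-respondents, both to reduce and to reveal response bias.
- **Limitations.** For the survey, section 9.9 names only the likelihood that more engaged or better educated professionals take part.

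**The concern.** Questions 1 to 15 of Appendix 2 are factual items on indications, dosing, switching, stopping before surgery, overdose and monitoring. The answers are in the Educational Material and the SmPC, and section 9.4 says the Educational Material goes to all physicians before edoxaban is available. A physician answering through a web link may have the source open. A physician answering by telephone has less opportunity.

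The survey is the instrument for a stated objective (section 8.1): the knowledge that the educational programme achieved. If some answers are looked up, the score partly measures access to the guide. Because mode follows preference, it may also differ between countries, specialties and rounds, which are the comparisons a reader of the report will make. An apparent difference in knowledge could then be partly a difference in mode, and the listed variables would not show it.

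**Working it through.** **1. The protocol's own figure.** Inputs from section 9.5: assumed proportion 85%, N = 100, 95% interval, lower bound stated as above 78%.

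Half-width = 1.96 × √(0.85 × 0.15 / 100) = 0.0700. Lower bound = 0.85 − 0.0700 = 0.7800.

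The plain two-sided normal (Wald) interval reproduces the statement (0.78002 unrounded). The sampling half-width to compare with is 7.0 points.

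**2. What the named controls can detect.**

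| Control in section 9.4 | What it addresses | Look-up during completion? | Mode effect? |
|---|---|---|---|
| First round at the site initiation visit | Reading before the survey | No | No |
| Respondents compared with non-respondents | Who takes part | No | No |

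A look-up effect arises among respondents while they answer. Neither control observes that.

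**3. Possible size.** The protocol gives neither the share answering by web nor a look-up rate, so both are assumptions. Let k be the true proportion with adequate knowledge, w the web share, and l the share of web respondents who look up and then answer correctly. Telephone respondents are assumed not to look up.

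Measured = k + (1 − k) × w × l, so k = (measured − w·l) / (1 − w·l).

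With measured = 0.85:

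| w | l | w·l | True k | Inflation (points) |
|---|---|---|---|---|
| any | 0 | 0 | 85.0% | 0 |
| 0.25 | 0.10 | 0.025 | 0.825/0.975 = 84.6% | 0.4 |
| 0.50 | 0.25 | 0.125 | 0.725/0.875 = 82.9% | 2.1 |
| 0.50 | 0.50 | 0.250 | 0.600/0.750 = 80.0% | 5.0 |
| 0.75 | 0.50 | 0.375 | 0.475/0.625 = 76.0% | 9.0 |
| 1.00 | 0.50 | 0.500 | 0.350/0.500 = 70.0% | 15.0 |

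Inflation equals 0.15 × w·l / (1 − w·l). It reaches the 7.0-point half-width when w·l = 0.07/0.22 = 0.32, that is, when about a third of all respondents look up and succeed. Below that, sampling error is the larger component.

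**4. Differences between groups.** If two groups share the same k and l but have web shares w₁ and w₂, the spurious difference is (1 − k) × l × (w₁ − w₂). With k = 0.80, l = 0.50 and web shares of 0.75 and 0.25, it is 0.20 × 0.50 × 0.50 = 5 points.

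**5. What a split by mode could show.** At N = 100 and 85% in both modes, the 95% half-width of the telephone-minus-web difference is:

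- 50/50 split: 1.96 × √(0.1275 × (1/50 + 1/50)) = 14.0 points
- 25/75 split: 1.96 × √(0.1275 × (1/25 + 1/75)) = 16.2 points

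Only a large gap would stand out, and self-selection of mode would confound even that.

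**The case against.** The strongest reply has four parts.

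- **Detail that belongs elsewhere.** An extra field and a table split are commonly left to the statistical analysis plan or the data management plan, and the list of breakdowns in section 9.7 is open. This stands for the table split. It does not stand for the instruction: the questionnaire is fixed in Appendix 2, and a later analysis plan cannot supply an instruction that respondents never received.
- **Little incentive to look up.** Physicians are told that they are not individually assessed and that results are reported only in aggregate. Ten of the eleven questions from 5 to 15 offer a don't-know option. This stands, and is a reason to regard low look-up rates as realistic.
- **Limited consequence.** The survey is descriptive. Section 9.5 sets no target threshold, so 85% is a precision assumption, and crossing it triggers nothing. Section 9.1 relies on chart data for prescribing behaviour. This stands and limits the weight of the point.
- **No direct contradiction.** The wording "thus minimizing the impact of any previous reading of the Educational Material by the physician" concerns earlier reading, and look-up while answering does not contradict it. This is correct. The overreach is in the broader response-bias claim that follows it in section 9.4.

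A reader might also infer that web completion is unsupervised, that scores are certainly inflated, that mode goes unrecorded, or that any bias could never be separated. The protocol supports none of these. The first round is tied to the site initiation visit, and the text does not say whether completion is supervised. Inflation could be zero. The stated contact preference and the unique link mean that mode may be known operationally although it is not a listed variable.

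**Conclusion.** The point holds in a limited form. Mode follows the physician's preference, nothing in the questionnaire discourages look-up, mode is not a listed survey variable, and the limitations do not mention either issue. Knowledge scores may be overstated, and group or round differences may partly reflect mode. The two controls named in section 9.4 cannot detect this, so its claim to reduce and reveal response bias is wider than they can deliver.

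The size is not known. Over web shares of 25% to 100% and look-up rates of 0% to 50%, inflation at a measured 85% is 0 to 15 points, and about 2 points in a middle case (half by web, a quarter of those looking up). These inputs are assumptions, and the upper end needs every physician to use the web and half of them to look up. Inflation exceeds the 7-point sampling half-width only when about a third of all respondents look up successfully. This is an inexpensive improvement to the instrument and the data captured. It does not show that the survey fails.

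**What to change.** 1. Add one line to the Appendix 2 introduction asking physicians to answer without consulting the Prescriber's Guide, the SmPC or other sources. Record the date it takes effect: wave I began in Q3 2016 (Table 5), so some of those physicians may already have been surveyed. Wave II starts from Q3 2017, after this version.
2. Add mode of completion (telephone or web), for each round, to the survey administration variables in section 9.3, III.1.
3. Keep each physician in the same mode in both rounds where possible.
4. Show knowledge results by mode as a descriptive diagnostic, and state that this is not a correction.
5. In section 9.4, narrow the bias claim to what timing and the respondent comparison can address. In section 9.9, add look-up during completion as a limitation.

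**Cost.** One sentence in the questionnaire, one administrative field, one table split and two short text edits. The instruction cannot be enforced online. Cells by mode will be small and confounded by self-selection. Introducing the line mid-study may slightly reduce comparability between waves, which is why its date should be recorded.

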9.5. Study Size

The medical records of approximately 200 patients will be studied per country (sample would be representative dependent on country-specific volumes of edoxaban prescriptions) to approximately 1,200 treated patients in total across the 6 targeted European countries.

For characterization of users including potential off-label use, we present the level of precision in different scenarios of available number of users of edoxaban for different prevalence of diseases/conditions. In general, the 95% level of confidence is adequate for a prevalence as low as 1% and 1,200 users of edoxaban.

The sample size has been estimated based on the precision of a percentage, that is, the width of the 95% confidence Interval (CI). Table 2 (see summary page 17) presents the precision in the estimate of the proportion of use of edoxaban out of the labelled indication for tentative proportions of 0.02, 0.03, 0.04, 0.05 (2%, 3%, 4%, 5%) and different sample sizes.

Table 6 - Precision of estimation for proportions of 0.02, 0.03, 0.04, 0.05 (2%, 3%, 4%, 5%) of off-label use and increasing sample size

	Proportion											
	0.02			0.03		0.04		0.05				
Sample Size	½ CI	L95%	U95%	½ CI	L95%	U95%	½ CI	L95%	U95%	½ CI	L95%	U95%
200	0.019	0.001	0.039	0.024	0.006	0.054	0.027	0.013	0.067	0.030	0.020	0.080
400	0.014	0.006	0.034	0.017	0.013	0.047	0.019	0.021	0.059	0.021	0.029	0.071
600	0.011	0.009	0.031	0.014	0.016	0.044	0.016	0.024	0.056	0.017	0.033	0.067
800	0.010	0.010	0.030	0.012	0.018	0.042	0.014	0.026	0.054	0.015	0.035	0.065
1000	0.009	0.011	0.029	0.011	0.019	0.041	0.012	0.028	0.052	0.014	0.036	0.064
1200	0.008	0.012	0.028	0.010	0.020	0.040	0.011	0.029	0.051	0.012	0.038	0.062

Note: CI: 95% of Confidence Interval (CI); ½ CI: distance from proportion to lower/upper limit of the two-sided 95% CI (equals half of the width of the CI); L95%; L95%: lower limit of the 95% CI; U95%: upper limit of the 95% CI.

Table 2 shows that the width of the 95% CI decreases as sample size increases; samples greater than 500 patients enable the estimation of the proportion of off-label use with an acceptable degree of precision. Increasing the sample size beyond 600 patients shows additional (though small) effects on the width of the 95% CI. Therefore, the current aim of recruiting 1,200 patients will assure to receive reliable results.

A sample size of 600 patients for instance will allow the detection of a rate of 5% of off-label with a precision of 1.7%, that is, the estimated proportion will be comprised between 3.3% and 6.7%. A sample size of 1,200 patients will allow for an even higher precision, as a rate of 5% of off-label is detected with a precision of 1.2%, that is, the estimated proportion will be comprised between 3.8% and 6.2%.

[figure not shown]

Figure 2 - Confidence Interval (CI) for half of CI width

In addition, it is estimated that approximately 100 physicians will have to complete the survey to allow reasonable precision around estimates of the physician's awareness and understanding levels.

In order to achieve robust results from the various statistical validation methods, it is recommended to have at least 10 physicians per questionnaire item/observation. This rule has been adopted as the standard for psychometric (fit for purpose) validation with its origin within the classical test theory of principal component analysis.⁴

No target thresholds for physicians reported awareness and understanding have been established in advance. However if it is assumed that 85% of physicians will demonstrate appropriate awareness and understanding of the survey. Given this, the lower bound of the 95% CI will be above 78% for a sample size of N=100.⁵

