3.1. List of Participating Centers and Countries

The following countries are planned to participate in the study: Germany, Italy, Switzerland, Belgium, the United Kingdom, Spain and Portugal.

A list of the principal investigators and all collaborating institutions and investigators is kept in a stand-alone document and can be made available upon request.

Table 1 - National Coordinators (Not applicable)

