The identity and contact details of the participants will only be used for scheduling and carrying out the survey. The survey will assess the physician's level of awareness and understanding of the content of the educational material/SmPC. All information collected during the course of the survey will be kept strictly confidential.

Study Size

The medical records of at least 100-200 patients will be studied per country (sample would be representative dependent on country-specific volumes of edoxaban prescriptions) for 600 to 1,200 treated patients in total across the 7 targeted European countries.

For characterization of users including potential off-label use, we present the level of precision in different scenarios of available number of users of edoxaban for different prevalence of diseases and conditions. In general, the 95% level of confidence is adequate for a prevalence as low as 1% and 1,200 users of edoxaban.

The sample size has been estimated based on the distance from the assumed proportion of patients with off-label use to the limits of the corresponding 95% confidence Interval (CI). Table 2 presents the precision in the estimate of the proportion of the off label use of edoxaban out of the labelled indication for tentative proportions of 0.02, 0.03, 0.04, 0.05 (2%, 3%, 4%, 5%) and different sample sizes.

Table 2 - Precision of estimation for proportions of 0.02, 0.03. 0.04, 0.05 (2%3%, 4% 5%) of off label use and increasing sample size

Sample Size Scenario

	pr	oportion =	0.02	proportion = 0.03			proportion = 0.04			proportion = 0.05		
sample size	½ CI	L95%	U95%	½ CI	L95%	U95%	½ CI	L95%	U95%	½ CI	L95%	U95%
200	0.019	0.001	0.039	0.024	0.006	0.054	0.027	0.013	0.067	0.030	0.020	0.080
400	0.014	0.006	0.034	0.017	0.013	0.047	0.019	0.021	0.059	0.021	0.029	0.071
600	0.011	0.009	0.031	0.014	0.016	0.044	0.016	0.024	0.056	0.017	0.033	0.067
800	0.010	0.010	0.030	0.012	0.018	0.042	0.014	0.026	0.054	0.015	0.035	0.065
1000	0.009	0.011	0.029	0.011	0.019	0.041	0.012	0.028	0.052	0.014	0.036	0.064
1200	0.008	0.012	0.028	0.010	0.020	0.040	0.011	0.029	0.051	0.012	0.038	0.062

Note: CI: 2-sided 95% Confidence Interval (CI); ½ CI: distance from proportion to lower/upper limit of the two-sided 95% CI (equals half of the width of the CI); L95%:

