9.2.1. Participating Sites

About 100 hospital- and office-based physicians (General Practitioners [GPs], internal medicine physicians and other specialists) in at least 7 Western European countries (Germany, Italy, Switzerland, the United Kingdom, Belgium, Spain and Portugal) are foreseen to participate in the study.

Country selection will take into account prescription volumes, the number of prescribers per capita, and favorable regulatory and ethical environment to conduct observational studies as well as the launch sequence of edoxaban in the different European countries. The sponsor may include additional European country(ies) based upon the actual use of edoxaban in initially-selected countries and to ensure selection reflects geographic representation among European countries.

Following the identification of the countries, an independent prescription data source (IMS LifelinkTM) will be used to identify a representative sample of the prescribers in each country. Based on these sources it is possible to retrieve general information on edoxaban number of prescribers per specialty and geographic region.

At least 100 prescribers of edoxaban will be recruited in 7 European countries following each country-specific product launch and the distribution of the health care professional (HCP) Educational Material. These could include GPs, cardiologists, internal medicine specialists (and other specialists) from a variety of settings (e.g., office-based vs. hospital-based, urban vs. rural).

Physicians participating in interventional programs for edoxaban will not be eligible to participate in the study. By applying this approach both representativeness and comprehensiveness of the sample in terms of types of prescribers are ensured.

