In the selected countries, available national prescription databases will be screened to identify geographic and edoxaban prescriber characteristics. Data from IMS LifeLinkTM database for dispensing data in the community care setting, or another appropriate data source, will identify prescribers of edoxaban. This data source will be complementary to the full study and will be obtained prospectively on a quarterly basis, during the study period. On a national level for the targeted countries, the distribution of regional location of the sites as well as the distribution of the prescribers' specialty will be provided. Therefore, IMS LifeLinkTM will be used to refine the a priori sampling strategy for the full study (using regional and specialty distribution of prescribers), and a posteriori to assess the representativeness of prescribers and patients included in the full study. This approach will contribute significantly to the enrolment of a more balanced population of edoxaban and alternative drugs prescribers at both the country and study level to cover broad indications. Potential sites for this DUS must meet the following criteria:

- Willing to provide a list of patients receiving edoxaban
- To allow/have access to patients' source data that are treated with edoxaban
- To be able to complete the study in the EDC system (only in exceptional cases paper CRFs are possible if no access to internet is provided)
- To be able to conduct the study adequately with respect to staff and time capacities.

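### Section 9.5 sizes the study for 6 countries but the protocol runs in 7, so about 200 per country and about 1,200 in total cannot both hold

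*Protocol*

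**What the plan says.** Section 9.5 (Study Size) sets the per-country size: "The medical records of approximately 200 patients will be studied per country". The same sentence ends with the total: "approximately 1,200 treated patients in total across the 6 targeted European countries". Between the two stands a parenthesis on allocation: "sample would be representative dependent on country-specific volumes of edoxaban prescriptions".

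The Study Size part of the Summary (section 4) gives other figures: "The medical records of at least 100-200 patients will be studied per country", with the same parenthesis, "for 600 to 1,200 treated patients in total across the 7 targeted European countries".

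On the number of countries, section 3.1 lists "Germany, Italy, Switzerland, Belgium, the United Kingdom, Spain and Portugal", which is seven. Section 9.2.1 foresees physicians "in at least 7 Western European countries". The title-page study information and the Setting part of the Summary name the same seven, and Table 5 has a row for each.

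On per-country output, section 9.7 describes use that departs from the product label overall and by country, and the Summary has inappropriate prescribing characterised separately per country. Other per-country analyses are planned only where reasonable. Section 9.2.2 allows the overall numbers of patients and sites to be adjusted to meet enrolment goals.

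**The concern.** The sizing sentence in section 9.5 contains three figures tied by one multiplication: size per country, number of countries and total. One of them, the number of countries, disagrees with the rest of the protocol. Once it is corrected, at least one of the other two must change, and the text does not say which.

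The Summary does not settle the matter. It has the right number of countries, a different per-country size and a total range that does not follow from them.

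Three practical things depend on the answer: whether enrolment is complete at 1,200 or at 1,400, how many charts each country and site is asked to abstract, and how precisely off-label use can be reported for a single country. The parenthesis adds an ambiguity, because a common size per country and a sample that depends on prescription volume are different allocations, and no rule says which applies.

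**Working it through.** **Inputs.** Section 9.5: 200 per country, 6 countries, 1,200 in total. Summary: 100 to 200 per country, 7 countries, 600 to 1,200 in total. Sections 3.1 and 9.2.1 and Table 5: 7 countries. Tables 2 and 6: two-sided 95% confidence intervals, with the half-width as the measure of precision.

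**Step 1: the total in section 9.5.** Total = size per country × number of countries.
- As written: 200 × 6 = 1,200. The stated total is reproduced, but only with six countries.
- With seven and 200 kept: 200 × 7 = 1,400, which is 200/1,200 = 16.7% above the stated total.
- With seven and 1,200 kept: 1,200/7 = 171.4, which is 28.6/200 = 14% below the stated per-country size.

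**Step 2: the range in the Summary.**
- Six countries: 6 × 100 = 600 and 6 × 200 = 1,200. This is exactly the stated range.
- Seven countries: 7 × 100 = 700 and 7 × 200 = 1,400.
- At the lower end, 600/7 = 85.7, so the average country would fall below the stated minimum of 100. This is a strict contradiction.
- The upper end is milder. A total of 1,200 over seven countries averages 171, which lies within 100 to 200. It is just not the upper end that the per-country range implies.

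**Step 3: the protocol's own precision figures.** Half-width = 1.96 × √(p(1 − p)/n).
- p = 0.05, n = 1,200: 1.96 × √(0.0475/1,200) = 0.0123. The protocol states 1.2 points.
- p = 0.05, n = 600: 0.0174. The protocol states 1.7 points.
- p = 0.05, n = 200: 0.0302. Table 6 has 0.030.
- All 24 half-widths in Table 6 reproduce to three decimals with this formula.

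The formula contains the total number of patients and not the number of countries. The pooled figures for 1,200 are therefore right under simple random sampling, whether those patients come from six countries or seven.

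**Step 4: precision by country at 5% off-label use.**

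| Patients in the country | Where the size comes from | Half-width |
|---|---|---|
| 200 | section 9.5 as written | 3.0 points |
| 171 | 1,200/7 | 3.3 points |
| 100 | minimum in the Summary | 4.3 points |
| 86 | 600/7 | 4.6 points |

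Tables 2 and 6 have no row below 200, so they do not show the precision at the smaller country sizes that the Summary permits.

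**The case against.** The strongest reply is that this is a stale count with little consequence. The amendment log records two countries removed and three added, which fits a 6 left over from before that change. The sizes are approximate, section 9.2.2 lets them be adjusted, and 1,200 is the consistent aim elsewhere. All of this is fair, and it is why the effect is modest. It does not remove the contradiction: a gap of 14% to 17% is more than rounding, and section 9.2.2 says that numbers may change, not how they are divided among countries.

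A second reply also stands. Table 6 is a ladder of total sample sizes, and nothing ties its 200 row to a country. The protocol sets no per-country precision target, so Table 6 is not wrong.

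A reader might infer more: that section 9.5 fixes equal quotas, that the pooled percentage therefore misrepresents European users, and that it must be weighted by prescription volume. The documents do not support this.
- Equal quotas are not fixed. The size is approximate, the Summary allows 100 to 200, and the parenthesis can be read as letting country sizes follow volume.
- Distortion needs both unequal volumes and off-label rates that differ by country, and the documents give neither. Suppose one country has 8% off-label use and the other six 4%. Equal country sizes then give an unweighted figure of (8 + 6 × 4)/7 = 4.6%. If the first country has 30% to 50% of prescriptions, the weighted figure is 5.2% to 6.0%. These inputs are invented, and with equal rates or equal shares the difference is zero.
- Weighting is commonly left to the SAP, which is not at hand. Section 9.2.1 uses the prescription data to refine the sampling beforehand as well as "a posteriori to assess the representativeness of prescribers and patients included in the full study". Those data are described as community-care dispensing data, while the study includes hospital physicians, so they may not supply suitable weights.

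**Conclusion.** The sizing statement in section 9.5 is wrong as written. With the seven countries of the current protocol, about 200 per country and about 1,200 in total are incompatible: the total becomes 1,400 or the average country size about 171. The Summary's range is also computed for six countries, and its lower end breaks its own minimum.

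The consequence is limited to the per-country results. If 1,200 is kept, the half-width at 5% widens from 3.0 to about 3.3 points for a country of average size, and to 4.3 points for a country at the Summary's minimum. These figures assume simple random sampling within a country and the normal approximation that the protocol itself uses. The pooled precision at 1,200 stands as stated.

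The allocation between countries is ambiguous, not shown to be biased. Neither an error in the pooled estimate nor a need for volume weighting follows from this document.

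**What to change.** - In section 9.5, change 6 countries to 7.
- State the same total and the same per-country size in section 9.5 and the Summary. One consistent choice is 1,200 in total, on average about 171 per country, with a minimum that fits the total. With a minimum of 100, for example, 7 × 100 = 700 patients are committed and 500 remain to be divided.
- Give the precision at the per-country sizes chosen, for example 3.3 points at 171 and 4.3 points at 100 for 5% off-label use. Tables 2 and 6 can stay as they are for the pooled sample.
- Say in one sentence whether country sizes are equal or follow prescription volume.

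Keeping 1,200 costs only wording. Keeping 200 per country means 200 more patients. At the 7.5 hours per patient estimated in section 14.1, which includes set-up time, that is 200 × 7.5 = 1,500 hours of site work. In return the pooled half-width at 5% falls from 1.23 to 1.14 points and the per-country half-width stays at 3.0.
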